Low Molecular Weight hEparin vs. Aspirin Post-partum (LEAP)

Version 1: October 25, 2020

Version 2: July 27 2021 – changes as per minor protocol change on randomization system and data collection table, indicated on the pink highlights with comment.

Version 2.1: September 13, 2021- reference list added, indicated on the yellow highlights.

Version 2.2: October 29, 2021 - Screening time changed in the table, Randomization section updated as per suggestions

Version 2.3: November 11, 2021- Screening time changed in the table from day -14 to day -1 to week -8 to day -1, Randomization section updated in the latest version of Protocol from September 29

Version 2.4: December 13, 2021- In 'Trial Schematic Table' data will be collected for concurrent medication at 3 month follow up.

Version 2.5: December 29, 2021- In 'Trial Schematic Table' Bleeding Assessment Score has been added for 3 week follow up, 6 week follow up, early discontinuation form.

Version 2.6: January 14, 2022- In 'Trial Schematic Table' Data for Quality Of Life Assessment will not be collected on dosing day.

Version 3: October 11, 2022- Study title changed to Low Molecular Weight hEparin vs. Aspirin Post-partum (LEAP)

Low Molecular Weight hEparin vs. Aspirin Post-partum (LEAP) Title

Low Molecular Weight hEparin vs. Aspirin Post-partum (LEAP)

Aim and Overall Objective

The principal question to be addressed, in a large definitive trial, is whether a combination of low molecular weight heparin (LMWH) and low dose aspirin is non-inferior to standard of care of LMWH for venous thromboembolism prophylaxis (VTE) postpartum. This single-center randomized pilot feasibility study will address enrollment, adherence and feasibility for the definitive trial.

Introduction

Expert opinion from the American Society for Hematology (ASH), the Royal College of Obstetricians and Gynecologists, UK, as well as the 'Society of Obstetricians and Gynecologists' guidelines recommends a minimum of 6 weeks of prophylactic LMWH for patients with a history of VTE or high-risk thrombophilias. This recommended duration is based on expert consensus and observational data that do not clearly define the risk of VTE and the risk reduction with LMWH therapy. LMWH requires daily subcutaneous injections, is associated with an increased risk of bleeding and is expensive. There are no randomized controlled trials (RCTs) determining the optimal duration of anticoagulation postpartum. A 2014 Cochrane review concluded that there is *insufficient evidence on which to base thromboprophylaxis in the pregnancy setting, and high-quality randomized trials are warranted* (Bain *et al.*, 2014).

A recent RCT randomized patients following total hip and knee arthroplasty (surgery associated with a high risk of VTE) to limited duration of prophylactic anticoagulation followed by aspirin (ASA) compared to the standard practice of prophylactic anticoagulation treatment. Limited duration of anticoagulation followed by ASA was found to be non-inferior to LMWH (Anderson *et al.*, 2018). The combination of standard prophylactic anticoagulation for a reduced duration followed by ASA may also be non-inferior for postpartum prophylaxis. This proposal is the first step to determine whether postpartum prophylactic LMWH for women requiring prophylaxis with 3 weeks of LMWH followed by 3 weeks of low dose ASA is non-inferior to 6 weeks of prophylactic LMWH. The safety of ASA in the antepartum period (Rolnik *et al.*, 2017; CLASP study, 1994) and during breastfeeding (Datta *et al.*, 2017) has been well established.

Background

For women not already receiving extended duration therapeutic anticoagulant therapy who have a history of VTE that was unprovoked or associated with a hormonal risk factor, the ASH guidelines recommend postpartum anticoagulant prophylaxis for 6 weeks. VTE occurring within 6 weeks postpartum affects 6.5% of pregnancies in women with a history of VTE (95% CI, 4.3%-9.7%) (Rodger *et al.*, 2014), compared with a risk of approximately 0.6 of every 1000 deliveries for the general population (Tepper *et al.*, 2014; Kourlaba *et al.*, 2016; Parunov *et al.*, 2015; Kamel *et al.*, 2014). Overall, the incidence during the 1st week postpartum is 9 in 10,000 deliveries, reducing to 2.5 and 1.5 in 10,000 by the 2nd and 3rd week postpartum, respectively (Tepper *et al.*, 2014). In women with a history of VTE who were treated with postpartum prophylaxis (LMWH, UFH), the risk of postpartum VTE was substantially lower at 1.7% (95% CI, 1.2%-2.7%) (Roger *et al.*, 2014), representing a decrement in risk similar to that seen with extended LMWH prophylaxis after high-risk orthopedic procedures (Hull *et al.*, 2001). In the presence of a high-risk thrombophilia and LMWH prophylaxis postpartum, the pooled VTE incidence was 0.2% (95% CI, 0%-1.2%).

In contrast to LMWH, which is expensive and requires daily subcutaneous injections, ASA is an inexpensive, generic, and widely available oral antiplatelet drug. Furthermore, in the postpartum period LMWH is associated with a 0.3% (95% CI: 0%-1%) risk of major bleeding events, 1.8% risk of skin reactions and wound complications after cesarean delivery. ASA use compared to placebo in the antenatal period did not demonstrate increased bleeding complications in 798 patients, with no gastrointestinal (GI) bleeding noted (Rolnik *et al.*, 2017), and in the orthopedic setting with a two-week administration post total knee

replacement, the GI bleeding was 1.7 per 1000 patient-years in the ASA group compared to 31.9 per 1000 patient-years with LMWH (Nielen *et al.*, 2016). Clinical trials and meta-analyses have suggested that ASA is non-inferior for the prevention of VTE in patients post- operatively (Anderson *et al.*, 2018; PEP trial, 2000; Antiplatelet Trialists' Collaboration, 1994). Notably, orthopedic patients are at particularly high risk of DVT/ PE within 90 days following total hip and knee replacement (incidence 5% and 2%, respectively), despite treatment with either warfarin, LMWH or ASA (Matharu *et al.*, 2020). ASA administered daily post-operatively has been shown to be non-inferior to LMWH when used for VTE thromboprophylaxis following these procedures (RR 0.76; 95% CI, 0.37- 1.56), and has a similar safety profile (Matharu *et al.*, 2020). Furthermore, Anderson *et al.*, 2018, NEJM, demonstrated clinical safety and non-inferiority of a combination of 5 days of rivaroxaban followed by 81mg of ASA for 30 days after total hip arthroplasty and 9 days after total knee arthroplasty.

It has been suggested that overall, the highest risk period for VTE in all postpartum women is between 1-3 weeks, with a sharp decline documented following this time period (Abdul Sultan *et al.*, 2014). The weekly distribution incidence of all VTEs within a 6 week period is 61.1%, 16.3%, 9.9%, 6.3%, 4.0% and 2.4% respectively, with an incidence of 9.41/10,000 in the 1st week, 2.58/10,000 in the 2nd , 1.62/10,000 in the 3rd, 1.00/10,000 in the 4th and 0.67 and 0.40/10,000 in the 5th and 6th week respectively (Tepper *et al.*, 2014). The median time for readmission with VTE in a retrospective study of 6,269,641 patients between 2013 and 2014 using a Nationwide Readmissions Database in the USA was 14 and 11.7 days for deep vein thrombosis and pulmonary thromboembolism, respectively (Wen *et al.*, 2018). This data clearly emphasizes the sharp reduction in risk of VTE one week after delivery, followed by a significantly lower risk 3-6 weeks postpartum.

Further supporting the reduction in risk of VTE after the first few weeks postpartum are plasma levels of progesterone and estrogen. The association between increased serum estrogen and progesterone levels and VTE is clearly described in the literature of oral contraceptive (OC) use. With 'low dose' OC containing < 50 μ g of estradiol, the risk of VTE is increased three to six-fold (World Health Organization). Furthermore, progestogens such as levonorgestrel have an up to a three-fold increase in VTE (Kemmeren *et al.*, 2001), and OC in the presence of obesity increased the risk 10-fold. Mechanisms postulated are a documented acquired resistance to activated protein C (Rosing *et al.*, 1997), and a hormone-induced venous stasis which in pregnancy coupled with endothelial damage and a hypercoagulable state are thought to lead to the 7-10 fold increase in daily risk of VTE antepartum and 15-35 fold postpartum. Plasma levels of progesterone one week postpartum have been noted to be 1.46 ± 1.53 nmol/L, which is less than the 5.00 ± 10.39 (nmol/L) in non- pregnant matched controls (Abou-Saleh *et al.*, 1998). Estrogen one week postpartum has also returned to non-pregnancy levels (124.40 ± 60.23 pmol/L vs 128.72 ± 395.39 pmol/L). The normalization of estrogen and progesterone to non-pregnancy levels at 1 week postpartum suggests a reduction in VTE risk.

Based on (A) the demonstrated non-inferiority of ASA as compared to LMWH in the orthopedic cohort of patients whose VTE risk is known to be high and (B) taking into account that the median time for VTE readmission postpartum is between 11.7 and 14 days suggesting that this is the risk period for VTE, (C) that pregnancy hormones have returned to normal by 1 week after delivery, and (D) LMWH is associated with a higher risk of bleeding than ASA, **I propose a pilot study to determine whether the duration of LMWH postpartum can be reduced to 3 weeks followed by ASA for a 3-week period.** The purpose of pilot studies is to determine the acceptability and feasibility of the treatment strategies. It is imperative to determine feasibility prior to embarking on a definitive study to identify barriers to recruitment and address clinical uncertainty, if any.

Study Design

This is a single-center pilot feasibility RCT comparing 3 weeks of LMWH followed by 3 weeks of ASA compared to standard care of 6 weeks of LMWH prophylaxis.

Inclusion Criteria: The inclusion criteria are to include all patients who are deemed to require prophylaxis for 6 weeks postpartum.

- 1) Personal history of VTE prior to pregnancy and not prescribed indefinite therapeutic anticoagulation (ASH guidelines).
- 2) Family history of VTE and antithrombin deficiency, protein C or protein S deficiency (ASH guidelines).
- 3) Combined thrombophilia or homozygous for factor V Leiden mutation or prothrombin gene mutation, regardless of family history (ASH guidelines).
- 4) > 18 years old
- 5) English speaking and able to provide informed consent

Exclusion criteria:

1. Pre-existing indication for therapeutic LMWH
2. Contraindication to ASA:
 - a. Known ASA allergy
 - b. Documented history of gastrointestinal ulcer
 - c. Known platelet count < 50x10⁹/L at any time during the current pregnancy or postpartum
3. Contraindication to LMWH, e.g. known allergy
4. Active bleeding at any site, excluding physiological vaginal bleeding
5. Patients with bleeding disorders for example hemophilia or von Willebrand disease
6. Known severe hypertension (SBP >200mm/hg and/or DBP >120mm/hg) during the current pregnancy or postpartum
7. Unable to provide or declining informed consent for data collection

Intervention:

Patients allocated to the LMWH and ASA strategy will receive a prophylactic dose of LMWH according to weight (< 100kg: Dalteparin 5000 units daily, Enoxaparin 40 mg daily, Tinzaparin 4500 units daily; > 100kg: Dalteparin 10,000 units daily, Enoxaparin 80mg daily, Tinzaparin 9000 U) by subcutaneous injection for 3 weeks followed by ASA 81 mg orally daily for three weeks. A clinic nurse will teach participants how to self-administer the LMWH injections.

Patients randomized to the LMWH strategy will receive a prophylactic dose of LMWH according to weight, daily for 6 weeks.

All participants will receive the first injection within 12 hours of delivery.

Randomization

Patients will be identified in the Hematology Clinic of the Special Program at Mount Sinai Hospital, where consent will be obtained. Patients will be randomized immediately following consent. Randomization has been developed for RedCap to allocate the patient into one of the two strategies in a 1:1 ratio, with the assistance of a statistician from Princess Margaret Hospital. Following delivery, the research assistant will dispense the assigned medication to the participant. Blinding or masking of treatment allocation will not be used in the pilot but a placebo control for ASA is intended for the definitive trial.

Baseline Assessment

Baseline assessments will be undertaken at the time of randomization and include age, weight, parity, indication for VTE prophylaxis, gestational age at delivery, medications and delivery complications. Baseline laboratory tests at the time of delivery will include complete blood count, serum creatinine level, coagulation profile and alanine aminotransferase. This limited testing is intended to reflect a pragmatic approach to this trial.

Primary Outcomes:

1. Potential enrollment rate (patients eligible)
2. Consent rates (patients approached/consent obtained/rationale for non-consent)
3. Adherence to study protocol (incidence and reasons for nonadherence, withdrawal of consent, rates of contamination and utilization of co-interventions).
4. Missing data

Secondary Outcomes:

1. VTE event rate three months following delivery
2. Bleeding event rate three months following delivery
3. Quality of life (QoL) assessment using the modified Duke Anticoagulation Satisfaction Scale (Appendix) at delivery and three and six weeks postpartum

Confirmation of VTE

VTE must be confirmed either by Doppler ultrasound or V/Q scan or computer tomography (CT). Imaging will not be performed on all patients, only those with symptoms. For the definitive trial, imaging will be adjudicated.

Bleeding outcomes

Bleeding will be reported according to the International Society on Thrombosis and Hemostasis (ISTH) scoring system (<https://bleedingscore.certe.nl/>) (Schulman *et al.*, 2005; Schulman *et al.*, 2009). Bleeding will be assessed at 3 and 6 weeks postpartum using a telephone questionnaire.

Follow up duration

All patients will be followed until 3 months postpartum. Patients will be contacted by telephone at 3 weeks, 6 weeks and 12 weeks after delivery.

Participant trial discontinuation

Participants may discontinue the study at any time. The participant will immediately discontinue the study medication, and the patient will be treated according to the standard of care. The patient will have a discontinuation telephone follow-up visit.

Statistical analysis

The analysis of this trial is mainly descriptive, as this is a pilot study to ensure adequate enrollment and adherence. All demographics and baseline characteristics will be summarized using mean, median, standard deviation, minimum and maximum for continuous variables, and frequency and percentages for categorical variables. The feasibility outcomes (primary outcomes) will be summarized using frequency counts and percentages with associated 95% confidence intervals.

The definitive trial is designed to show the non-inferiority of a combination of LMWH and ASA over LMWH in decreasing the incidence of composite VTE. However, for the pilot study, the clinical endpoints will only be presented using descriptive statistics. In the definitive trial, VTE, bleeding, and

event-free outcomes will be compared between the two arms using a stratified log-rank test. A non-inferiority margin of 1.0 % will be used based on expert opinion. Statistical analysis will be carried out using SPSS statistical software.

The feasibility trial will be deemed a success and will proceed to a full trial under the current protocol if all the criteria below are met:

- Participant recruitment is > 60%
- Participant adherence to study drug > 80%
- Compliance with study procedures > 80%
- Proportion of participants lost to follow up <25%

Sample size calculation: I plan to recruit 50 patients, 25 patients treated according to each strategy. The outcomes from these patients will be included in the definitive trial.

Recruitment rate: Recruitment is anticipated to be completed in 18 months as we anticipate to enroll 1 patient/week.

Trial registration: The trial will be registered at www.clinicaltrials.gov.

Data Management: Appropriate training and security measures will be completed. The case report form will be developed electronically and piloted. All patient-related information, including case report forms, will be kept strictly confidential. All records will be kept in a secure, locked location, and only research staff will have access to the records. Patients will be identified only by means of a coded number specific to each patient. All computerized databases will identify patients by numeric codes only, and will be password protected and housed in a locked office.

Data Safety Monitoring Committee: A data safety monitoring board will be assembled, consisting of one hematologist and one obstetrician. Any VTE or bleeding event will be reviewed by this committee.

Ethics: The study will be submitted for research ethics board approval. Virtual consent during the current COVID-19 pandemic is currently feasible and is an option for this trial.

Safety: I will be responsible for ensuring that the patient or her substitute decision-maker understands the risks and benefits of participating in the study, answering any questions the patient or family member may have throughout the study and sharing any new information in a timely manner that may be relevant to the patient's willingness to continue her participation in the trial. All study participants will be informed of the objectives of the study and the potential risks. Consent forms will also discuss the benefits and risks of this pilot trial and the definitive study. All patients will be informed of the signs and symptoms of VTE that would necessitate emergency room visits as participants in both arms may develop a VTE.

Significance: This single center pilot feasibility study will address enrollment, adherence of two anticoagulant strategies postpartum in women who require prophylaxis with LMWH. The results of this study will be used to design a large definitive multicentered trial. All clinical outcomes from the pilot study will be used to inform the final trial design. Demonstrating the non-inferiority of ASA and LMWH to LMWH will lead to a shorter course of LMWH postpartum, potentially reducing bleeding risk, need for subcutaneous injections as well as cost while improving quality of life. If the definitive trial does not show inferiority, the results will provide evidence that six weeks of postnatal thromboprophylaxis is warranted.

Trial Schematic Timeline

Participant	Screening Week -8 to Day -1	Dosing Day 1	3-week phone call ± 5 days	6-week phone call (end of study) ± 5 days	3-month phone call ± 5 days	Early discontinuation visit
Informed Consent	X	---	---	---	---	---
Inclusion / Exclusion criteria and Eligibility	X	---	---	---	---	---
Baseline demographics	X	---	---	---	---	---
Concurrent medications	X	---	X	X	X	X
Weight/BMI	X	X	X	X	X	X
Delivery Data: Type of Delivery/ Complications	---	X	---	---	---	---
Laboratory Data: Complete blood count / Creatinine / INR / aPTT / ALT	---	X	---	---	---	---
Drug dispensation	---	X	---	---	---	---
Adherence assessment	---	---	X	X	---	X
Bleeding Assessment Score	---	---	X	X	---	X
Quality of life assessment	---	---	X	X	---	X

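### The bleeding outcome is defined at three months, but no bleeding questionnaire is scheduled after week 6 for women who stay in the study

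*Protocol*

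**What the plan says.** Four places in the Protocol bear on this point.

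- **Secondary Outcomes, item 2** sets the time frame: "Bleeding event rate three months following delivery".
- **Bleeding outcomes** sets the assessment times: "Bleeding will be assessed at 3 and 6 weeks postpartum using a telephone questionnaire".
- **Follow up duration** provides a later contact: "Patients will be contacted by telephone at 3 weeks, 6 weeks and 12 weeks after delivery".
- **Trial Schematic Timeline** has a row "Bleeding Assessment Score", marked at the 3-week call, the 6-week call and the early discontinuation visit. In the column "3-month phone call ± 5 days" that row shows a dash. Only concurrent medications and weight/BMI are marked there.

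The version history matches the current table. The entry for version 2.5 reads "Bleeding Assessment Score has been added for 3 week follow up, 6 week follow up, early discontinuation form" and does not name the 3-month call. The entry for version 2.4 shows that the 3-month column was considered for other items: "data will be collected for concurrent medication at 3 month follow up".

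**The concern.** The outcome definition and the data collection plan disagree. The text and the schedule agree with each other that the bleeding questionnaire stops at week 6, and both conflict with a three-month outcome. A rate reported at three months would combine solicited events up to week 6 with whatever happens to be reported afterwards.

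Within the pilot the stakes are small. Clinical endpoints are only described, and none of the four success criteria in Statistical analysis uses bleeding. The larger issue is what follows. Under Statistical analysis, a successful pilot leads into the full trial on the present protocol, and bleeding is compared there by a stratified log-rank test. Under Sample size calculation, the pilot women's outcomes are to form part of that trial. Their bleeding follow-up would then have to be censored at about week 6, or be treated as complete to three months on the strength of unsolicited reports. The second choice would understate the three-month rate if any late bleeds went unreported.

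**Working it through.** The Protocol gives no figure for this point to reproduce. The check compares the passages and then measures the uncovered interval.

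**Step 1. Is the blank cell real?** The dash at the 3-month call could be a table-reading fault. Two other places rule that out: the Bleeding outcomes text independently names weeks 3 and 6, and the version 2.5 entry lists the same three contacts as the table.

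**Step 2. Does another scheduled contact fill the gap?** The early discontinuation visit applies only to women who discontinue. It gives nothing between week 6 and month 3 for those who stay in. The 3-month call takes place, but no bleeding item is marked for it.

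**Step 3. Inputs for the interval.**
- Delivery is day 0 (assumption).
- The 6-week call is on day 42 ± 5, so between days 37 and 47 (Trial Schematic Timeline).
- The outcome window ends on day 84 if three months means 12 weeks (Follow up duration), or about day 91 if it means three calendar months (assumption).
- Planned treatment runs over about days 0 to 42 in both arms (Intervention: six weeks of LMWH, or three weeks of LMWH and then three of aspirin).

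**Step 4. Share of the window after the last scheduled bleeding assessment** = (window end − day of the 6-week call) / window end.

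| Case | Calculation | Share |
|---|---|---|
| 12-week window, call on day 42 | (84 − 42)/84 = 42/84 | 50.0% |
| 91-day window, call on day 42 | (91 − 42)/91 = 49/91 | 53.8% |
| Lowest: 12-week window, call on day 47 | (84 − 47)/84 = 37/84 | 44.0% |
| Highest: 91-day window, call on day 37 | (91 − 37)/91 = 54/91 | 59.3% |

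**Step 5. How much of this is on treatment?** With the call on day 42 or later, none of the planned treatment period. With the call on day 37, 42 − 37 = 5 planned treatment days are left over. That is 5/42 = 11.9% of planned treatment, and 5/54 = 9.3% of the unassessed days in a 91-day window.

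**Step 6. After adding the bleeding score to the 3-month call.** If the call and the outcome window share one definition, the earliest permitted call falls 5 days before the window ends. The unassessed share is then at most 5/84 = 6.0% or 5/91 = 5.5%, and 0% if the call is at or after the window end. If the definitions differ, with a call centred on day 84 and a window ending on day 91, the earliest call is on day 79 and the share is (91 − 79)/91 = 13.2%. The definition therefore needs to be fixed together with the mark.

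**The case against.** The strongest reply is that the outcome is an event rate, and nothing restricts it to events found by questionnaire. Women are followed to three months and telephoned at 12 weeks, and the Data Safety Monitoring Committee section has every bleeding event reviewed, with no cut-off at week 6. The schedule has no row for VTE at any contact, although VTE is also a three-month outcome, so it is evidently not a full list of how events are captured. The case report form is not shown.

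This stands in part. Late bleeds are not certain to be lost, and the claim here is limited to what the questionnaire yields. But committee review is not a means of collection: no instrument or time is given for finding events after week 6. Bleeding also differs from VTE. For VTE the schedule is silent and nothing in the text contradicts a three-month outcome, so that is at most a point to clarify. For bleeding the row exists and is explicitly blank at 3 months, and the text agrees with the blank.

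A second reply concerns weight. The uncovered time is almost all off treatment. The Background gives a 0.3% risk of major bleeding on postpartum LMWH (95% CI 0% to 1%), so 50 women would have 50 × 0.003 = 0.15 expected major bleeds, or 0.5 at the upper limit, and fewer after week 6 if risk is no higher off treatment. This is fair for major bleeding, but the figure does not cover minor bleeding.

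A third reply is that the definitive trial can be redesigned, since the Significance section says the pilot will inform its design, and that censoring at a planned week-6 call costs person-time rather than causing evident bias. Both points are right. However, redesign cannot recover late bleeding data that were not asked for in the pilot women, and censoring at week 6 would concede that their data do not support a three-month rate.

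**Conclusion.** The inconsistency is real and should be fixed. The stated outcome window is three months, while scheduled bleeding assessment ends at week 6 for women who stay in the study. Between 44% and 59% of the window is left without a scheduled bleeding assessment, or 50% to 54% with the call on time. These shares rest on delivery as day 0 and on three months meaning 84 or 91 days. They measure calendar time, not lost events. The Protocol gives no bleeding rate after week 6, so the number of missed events cannot be estimated.

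The effect on the pilot's own conclusions is modest. The effect on the definitive trial cannot be sized, because its analysis horizon is not stated. This is not a matter that an analysis plan could settle: it can define how a rate is computed, but it cannot supply data that the schedule does not collect.

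**What to change.** Choose one of two options.

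1. **Keep the three-month outcome.** Mark the bleeding score at the 3-month call, have it ask about the whole period since the 6-week call, and change the Bleeding outcomes text to weeks 3, 6 and 12. State whether three months means 12 weeks or three calendar months, so that the call and the outcome window end together. The unassessed share then falls to between 0% and about 6%.
2. **Redefine secondary outcome 2 as the bleeding event rate at 6 weeks.** This matches the data as now scheduled and covers planned treatment, apart from up to 5 days when the 6-week call is made early. It gives up scheduled information on later bleeding, and the bleeding and VTE outcomes would then have different horizons.

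The first option costs one schedule mark and a wording change on a call already planned, with no new visit. The second costs a wording change only. As a clarification outside this finding, a short VTE question could be added to the same scheduled calls, including the one at three months.

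### For the definitive trial, the protocol pairs a 1.0% non-inferiority margin with a log-rank test that does not use it, and misstates what failing to show non-inferiority would mean

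*Protocol*

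**What the plan says.** All quotations are from the protocol.

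- **Aim of the definitive trial** (Statistical analysis): "The definitive trial is designed to show the non-inferiority of a combination of LMWH and ASA over LMWH", with composite VTE as the outcome.
- **Test and margin** (same section): the outcomes will be "compared between the two arms using a stratified log-rank test. A non-inferiority margin of 1.0 % will be used based on expert opinion". No other comparative test is named. The text does not say how the margin enters the comparison, on what scale it is measured, or at what time. The only time point given for a VTE outcome is in Secondary Outcomes: "VTE event rate three months following delivery".
- **Conclusions to be drawn** (Significance), in two consecutive sentences: "Demonstrating the non-inferiority of ASA and LMWH to LMWH will lead to a shorter course of LMWH postpartum", and then "If the definitive trial does not show inferiority, the results will provide evidence that six weeks of postnatal thromboprophylaxis is warranted".
- **Link from pilot to definitive trial.** If the feasibility criteria are met, the study "will proceed to a full trial under the current protocol if all the criteria below are met", and the Sample size paragraph adds "The outcomes from these patients will be included in the definitive trial". Against that, Significance says "The results of this study will be used to design a large definitive multicentered trial". The Randomization section plans an aspirin placebo for the later trial, and Confirmation of VTE says its imaging will be adjudicated.

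**The concern.** A non-inferiority claim needs a comparison that takes the margin into account. The standard log-rank test asks whether the two event-time curves are equal. A non-significant result shows neither that they are equal nor that the excess is below 1.0 point. If its p-value were taken as the answer, a trial that had not met its margin could be read as a success.

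The Significance section has a separate problem. Read literally, a trial that finds no inferiority of the shorter strategy supports six weeks of LMWH, which is the opposite of the sentence before it. The likely intention is 'does not show non-inferiority'. That version still treats an inconclusive result as positive evidence for the comparator.

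**Working it through.** The protocol gives no sample size, alpha, power or design event rate for the definitive trial, so it has no figure to reproduce. What follows is illustration.

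**Inputs**
- Margin: 1.0%, read as an absolute difference of 0.010 (assumption; the scale is not stated).
- Control VTE risk: 1.7%, with range 1.2% to 2.7%. This is the estimate and 95% CI in Background for women with prior VTE given postpartum prophylaxis. The protocol does not name it as a design rate, so its use is an assumption.
- Allocation 1:1, as in the pilot (assumed to carry over).
- One-sided alpha 0.025, which corresponds to two-sided 95% limits; power 80% or 90% (assumptions).

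**Step 1. Can the margin be carried into a log-rank test?** A log-rank test shifted to a hazard-ratio margin exists, but the protocol states no such ratio. With control risk p, the ratio equivalent to a 1.0-point excess is ln(1 - p - 0.01) / ln(1 - p):

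| Control risk | Equivalent hazard ratio |
|---|---|
| 1.2% | 1.84 |
| 1.7% | 1.60 |
| 2.7% | 1.38 |

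The conversion therefore depends on a control risk that the protocol does not fix.

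**Step 2. What size of trial does the margin imply?** With equal true risks, n per arm = (1.960 + z)² × 2p(1 - p) / 0.01², where z is 0.842 for 80% power and 1.282 for 90%. At 1.7% and 80% power: 7.849 × 2 × 0.017 × 0.983 / 0.0001, or about 2,624.

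| Control risk | 80% power | 90% power |
|---|---|---|
| 1.2% | 1,862 | 2,492 |
| 1.7% | 2,624 | 3,512 |
| 2.7% | 4,124 | 5,521 |

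**Step 3. Do the test and the margin answer the same question at that size?** Take 45 v 58 events in 2,624 per arm.
- Risks: 45/2,624 = 1.715% and 58/2,624 = 2.210%. Difference: 0.495 points.
- SE = √[(0.01715 × 0.98285 + 0.02210 × 0.97790) / 2,624] = 0.383 points.
- z = 0.495 / 0.383 = 1.29, p about 0.20. An unstratified log-rank test, with event times drawn from the weekly distribution in Background, gives p of 0.19 to 0.20.
- 95% CI: 0.495 ± 1.96 × 0.383 = -0.26 to 1.25 points.

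The test is not significant and the upper limit exceeds 1.0, so non-inferiority is not shown. With an observed control risk of 1.7% at this size, the same combination arises for any observed excess between about 0.27 points (where the upper limit reaches 1.0) and 0.77 points (where the lower limit reaches 0).

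**Step 4. Does failing to show non-inferiority support six weeks?** Suppose both true risks are 1.7%, with 2,624 per arm.
- SE = √(2 × 0.017 × 0.983 / 2,624) = 0.357 points.
- P(upper limit below 1.0) = Φ(1.0 / 0.357 - 1.96) = Φ(0.84) = 0.80.
- P(failure) is about 0.20. This is simply the complement of 80% power; at 3,512 per arm it is 0.10.

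Identical strategies would thus fail one time in five, and the Significance sentence with 'non-' restored would count each failure as evidence for the longer course.

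**The case against.** The strongest reply is that this is a pilot whose clinical endpoints are only described, and that the text on the definitive trial is a sketch. That largely stands. The later trial is to be multicentre, with an aspirin placebo and adjudicated imaging, and its design is to draw on the pilot's results. The current single-centre, open-label protocol cannot run it unchanged. A reader might infer from "will proceed to a full trial under the current protocol if all the criteria below are met" that the log-rank rule is already binding, but the other sections do not support that. No pilot result is affected.

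A second reply is that the protocol never says that the log-rank p-value decides non-inferiority; test and margin stand in adjacent sentences. That is fair. The defect is that the only comparison named cannot serve the stated aim and nothing connects it to the margin. An analysis plan could add the link, but it would not correct the protocol's own conclusion in Significance.

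A third reply is that the Significance sentence is a slip in a motivational paragraph. Probably so, but Step 4 shows that the obvious correction is not enough.

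Two stronger readings should be resisted. A reader might infer that no hazard ratio could ever stand in for the margin; one can, once an overall control risk is fixed. A reader might also infer that 1.0% is too wide because both arms receive LMWH for the first three weeks. The protocol compares whole strategies and does not claim that aspirin reproduces the late effect of LMWH, so there is no statement there to correct.

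**Conclusion.** The point holds as a minor one, confined to the text on the definitive trial. Two statements are wrong as written: a non-inferiority aim is served by a test that does not use the margin, and the conclusion in Significance is inverted and remains unsound once repaired in the obvious way.

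The mismatch appears at the size the margin would itself imply, not only in trials that are far too small or too large. The figures rest on an absolute margin, a 1.7% control risk, one-sided 0.025, 80% power, 1:1 allocation and little censoring. Over control risks of 1.2% to 2.7% the implied size at 80% power runs from 1,862 to 4,124 per arm. The 20% failure rate under equality follows from 80% power whatever the control risk.

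**What to change.** **Statistical analysis.** State that 1.0% is an absolute difference in VTE risk at a named time; three months after delivery is the only VTE outcome time the protocol gives. Declare non-inferiority if the upper confidence limit of the (stratified) Kaplan-Meier risk difference at that time is below 1.0 point. Keep the stratified log-rank test as supportive.

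**Significance.** Replace the second of the two sentences with wording to this effect: failure to show non-inferiority is inconclusive; only a confidence interval that excludes zero in favour of six weeks of LMWH is evidence of excess VTE with the shorter strategy.

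**Cost.** Wording only. Pilot conduct, data and analysis do not change, and the margin can stay. The downside is a narrower claim, and a fixed-time risk difference ignores when events occur; the supportive log-rank test partly covers that.
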